## 11.11 SWEETCH APP FEATURES QUESTIONNAIRE

## Sweetch App Features Questionnaire (23-item)

Please respond to each question from strongly disagree to strongly agree.	Strongly Disagree	Disagree	Neutral	Agree	Strongly Agree
1. The Sweetch App push notifications (messages) helped me to achieve my goals in the program	 1	 2	 3	 4	 5
2. The Sweetch App "My Achievements" feature helped me to achieve my goals in the program.	 1	 2	 3	 4	 5
3. The Sweetch App "My Challenges" feature helped me to achieve my goals in the program.	 1	 2	 3	 4	 5
4. The Sweetch app "My Competitions" feature helped me to achieve my goals in the program.	 1	 2	 3	 4	 5
5. The Sweetch app "My Leaderboard" feature helped me to achieve my goals in the program.	 1	 2	 3	 4	 5
6. The Sweetch app "My Supporter" feature helped me to achieve my goals in the program.	 1	 2	 3	 4	 5
7. The Sweetch app "T2D Prevention Lessons" helped me to achieve my goals in the program.	 1	 2	 3	 4	 5
8. The Sweetch app "Activity Tracking" helped me to achieve my goals in the program.	 1	 2	 3	 4	 5
9. The Sweetch app "Weight Tracking" helped me to achieve my goals in the program.	 1	 2	 3	 4	 5
10. The Sweetch app "Habits" feature helped me to achieve my goals in the program.	 1	 2	 3	 4	 5
11. The Digital Body Weight scale helped me to achieve my goals in the program.	 1	 2	 3	 4	 5
12. The Sweetch app accurately measured my physical activity overall.	 1	 2	 3	 4	 5

13. The Sweetch app did not capture certain types of physical activity that I performed.	 5	 4	 3	 2	 1
14. I would have liked to be able use a wearable fitness tracker with the Sweetch app.	 5	 4	 3	 2	 1
15. The push notifications I received felt personalized (i.e. tailored to me).	 1	 2	 3	 4	 5
16. The push notifications came to me at the right time in the day.	 1	 2	 3	 4	 5
17. The push notifications usually came to me when I was in the right place to be able to respond.	 1	 2	 3	 4	 5
18. The push notifications came at the right frequency/amount .	 1	 2	 3	 4	 5
19. It felt like the recommendations that I received in the push notifications were coming from a human coach .	 1	 2	 3	 4	 5
20. I usually ignored the push notifications.	 5	 4	 3	 2	 1
21. I found the push notifications annoying or bothersome .	 5	 4	 3	 2	 1
22. Please provide any comments/feedback regarding the Sweetch app overall or its individual features.					

	Not at all likely likely										Extremely	
23. How likely is it that you would recommend the Sweetch Digital Diabetes Prevention Program to a friend or colleague?	 0	 1	 2	 3	 4	 5	 6	 7	 8	 9	 10	

**Scoring:** Sum up responses to items 1 to 21, divide by 105 and multiply by 100 to calculate score out of 100%. Range of scores 20% (lowest usability/acceptability) to 100% (highest usability/acceptability)

**Net Promoter Score (Q. 23) Scoring:**

The Net Promoter Score is calculated based on responses to a single question: *How likely is it that you would recommend the Sweetch digital diabetes prevention program to a friend or colleague?* The scoring for this answer is most often based on a 0 to 10 scale. A score of 0-6 is considered a detractor, 7-8 passive, and 9-10 a promoter. The Net Promoter Score is calculated by subtracting the % promoters - % detractors = NPS.

## 11.12 WHO-5 WELL-BEING INDEX

The 5-item WHO-5 index is a widely used questionnaire to assess subjective psychological well-being.

**Please indicate for each of the 5 statements which is closest to how you have been feeling over the past 2 weeks.**

Over the past 2 weeks...	All of the time	Most of the time	More than half the time	Less than half the time	Some of the time	At no time
... I have felt cheerful and in good spirits	 5	 4	 3	 2	 1	 0
... I have felt calm and relaxed	 5	 4	 3	 2	 1	 0
....I have felt active and vigorous	 5	 4	 3	 2	 1	 0
...I woke up feeling fresh and rested	 5	 4	 3	 2	 1	 0
... my daily life has been filled with things that interest me	 5	 4	 3	 2	 1	 0

Scoring: The raw score ranging from 0 to 25 is multiplied by 4 to give the final score from 0 representing the worse imaginable well-being to 100 representing the best imaginable well-being.

### 11.13 LOCAL DPP DATA COLLECTION

Participating DPPs will be asked to enter the following data for participants referred to their program using a RedCap electronic data capture form:

Organization Code (assigned by CDC)	
Delivery Mode	 1= In-person
	 2= On-line (*Not permitted for trial)
	 3= Distance learning (**Only synchronous video/phone conference will be permitted)
Session Type	 C= Core Session
	 CM= Core maintenance session
	 MU-C= make-up sessions in the core phase
	 MU-CM= make up session in the core maintenance phase
Session Date	MM/DD/YY
Participant's weight (recorded to nearest lb.)	
Participant's physical activity (in minutes).	Number of self-reported minutes of moderate or brisk PA participant completed in the preceding week. If a participant reports doing no activity during the preceding week, then zero (0) minutes should be recorded.
Curriculum Used:	 2021 National DPP
	 Prevent T2

Curriculum Topic(s) covered: select all that apply.	
2012 National DPP Curriculum	PreventT2 Curriculum
Core Phase (Months 1-6)	
 Welcome to the National Diabetes Prevention Program	 Program Overview & Introduction to the Program
 Being Active- A Way of Life	 Get Active to Prevent T2
 Move Those Muscles	 Track Your Activity
 Be a Fat and Calorie Detective	 Track Your Food
 Three Ways to Eat Less Fat and Fewer Calories	 Eat Well to Prevent T2
 Jump Start Your Activity Plan	 Get More Active
 Tip the Calorie Balance	 Burn More Calories Than You Take In

 Healthy Eating	 Shop and Cook to Prevent T2
 You Can Manage Stress	 Manage Stress
 The Slippery Slope of Lifestyle Change	 Find Time for Fitness
 Make Social Cues Work for You & Talk Back to Negative Thoughts	 Cope with Triggers
 Heart Health from months 7-12	 Keep Your Heart Healthy
 Problem Solving	 Take Charge of Your Thoughts
 Taking Charge of What's Around You	 Get Support
 Four Keys to Healthy Eating Out	 Eat Well Away from Home
 Ways to Stay Motivated	 Stay Motivated to Prevent T2
Core Maintenance Phase (Months 7-12)	
 Welcome to Sessions 7-12	 N/A
 Balance Your Thoughts for Long-Term Maintenance	 When Weight Loss Stalls
 Staying on Top of Physical Activity	 Take a Fitness Break
 Stepping up to Physical Activity	 Stay Active Away from Home
 A Closer Look at Type 2 Diabetes	 More About T2
 More Volume, Fewer Calories	 More About Carbs
 Fats- Saturated, Unsaturated, and Trans Fat	 Eat Well to Prevent T2 from Months 1-6
 Healthy Eating – Taking it One Meal at a Time & Food Preparation and Recipe Modification	 Have Healthy Food You Enjoy
 Stress and Time Management	 Get Enough Sleep
 Preventing Relapse	 Get Back on Track
 Handling Holidays, Vacations, and Special Events	 Eat Well Away from Home from months 1-6
 Heart Health	 Stay Active to Prevent T2
 Healthy Eating with Variety and Balance	 Shop and Cook to Prevent T2 from months 1-6
 Looking Back and Looking Forward	 Prevent T2- for Life!

**11.14 HEALTHCARE UTILIZATION**

How many times did you visit your primary care provider in the past 6 months?	
How many times did you visit a non-primary care specialist in the past 6 months?	
Why did you see a non-primary care specialist?	
How many times were you hospitalized in the last 6 months?	
Why were you hospitalized?	
How many times did you go to the emergency department in the past 6 months?	
Why did you visit the emergency department?	
What is the name of your primary care provider?	
What is your primary care provider's address?	

## 11.15 HOME STUDY VISIT SAFETY PROCEDURES (JHU SITE ONLY)

For participants recruited from the JHU site, the option of study visits conducted in the participant's home will be provided to increase recruitment and retention. Community-based research is generally safe but there are risks. The following procedures will be followed to ensure that the privacy/confidentiality of the participant and that the safety and security of all staff are protected in the rare event of urgent or emergency situations.

### **Participant Privacy/Confidentiality**

All home visits will only be conducted by Johns Hopkins study team members. No non-study team members will be present for the home visit aside from the study participants (and residents of the home) themselves.

Prior to the home study visit, the research coordinator will inform the participant that informed consent will be obtained during the home visit and that ensuring privacy and confidentiality in the home will be the participant's responsibility.

### **COVID-19 Safety Plan**

See Section 11.19

### **Reportable Situations**

The informed consent form will specify the research team will be required to i) report any information regarding potential child abuse or neglect reported by the participant or observed at the home during the research visit and ii) report if there is a reasonable suspicion, based on information provided by the participant or observed during the research visit at the home, that the participant may present a danger or home to others or that they participant may harm themselves unless protective measures are taken. It will be communicated that the study team is not directly seeking this information as part of the study.

### **Daylight Hours**

Study visits will be conducted so that the entire visit can be completed during daylight hours.

### **Emergencies and Urgent Matters**

If an emergency or urgent matter occurs, the staff member must call the PI, [name]. If unable to reach one of the PIs, the staff member will call the Study Program Manager, followed by Co-PIs. The staff member should continue to call until s/he reaches a study team member. If an important but non-urgent matter arises, staff members will call a supervisor or PI.

### **Study Cell Phones**

All staff members working in the community, clinic, or with patients after-hours are required to program the office and cell phone numbers for the Study PIs, research coordinator(s), and supervisor(s) into their study provided cell phones. It is recommended that they also program the contact information of their co-workers assigned to the same study or studies as they are. All staff members must ensure that their study-provided cell phone is charged and functioning before going into the community. Staff driving for work must follow state driving laws in regards to the use of a mobile phone.

### **Staff Safety Concerns**

All staff members are encouraged to raise safety concerns during weekly meetings. Discussing concerns, experiences, situations, and possible solutions will benefit the entire staff. If a staff member has an urgent concern or prefers to speak in private, s/he may call the PIs or supervisor with any safety concern.

### **Perceived Unsafe Situation**

Upon arriving at a participant appointment or an off-campus meeting, if a staff member deems the situation unsafe, s/he may leave the location. As soon as s/he is safely able to do so, s/he must contact the PIs or supervisor to inform them of the situation.

### **No Tablets or Computers**

Survey forms will be printed out in advance of the visit and data will be recorded on paper. An electronic survey will also be sent out in advance of the visit for participants who are willing and able to complete the survey electronically. This will minimize the amount of time spent in the participant's home. If data are collected on paper, results will be transcribed after the visit into the electronic data capture form. This will minimize the potential for theft of tablets and computers. In addition, Wi-Fi access cannot be guaranteed in the participant's home.

## 11.16 PREDIABETES RISK TEST

# Prediabetes Risk Test

## 1. How old are you?

Younger than 40 years (0 points)  
40–49 years (1 point)  
50–59 years (2 points)  
60 years or older (3 points)

Write your score in the boxes below

## 2. Are you a man or a woman?

Man (1 point)    Woman (0 points)

## 3. If you are a woman, have you ever been diagnosed with gestational diabetes?

Yes (1 point)    No (0 points)

## 4. Do you have a mother, father, sister, or brother with diabetes?

Yes (1 point)    No (0 points)

## 5. Have you ever been diagnosed with high blood pressure?

Yes (1 point)    No (0 points)

## 6. Are you physically active?

Yes (0 points)    No (1 point)

## 7. What is your weight category?

(See chart at right)

Total score:

Height	Weight (lbs.)		
4'10"	119-142	143-190	191+
4'11"	124-147	148-197	198+
5'0"	128-152	153-203	204+
5'1"	132-157	158-210	211+
5'2"	136-163	164-217	218+
5'3"	141-168	169-224	225+
5'4"	145-173	174-231	232+
5'5"	150-179	180-239	240+
5'6"	155-185	186-246	247+
5'7"	159-190	191-254	255+
5'8"	164-196	197-261	262+
5'9"	169-202	203-269	270+
5'10"	174-208	209-277	278+
5'11"	179-214	215-285	286+
6'0"	184-220	221-293	294+
6'1"	189-226	227-301	302+
6'2"	194-232	233-310	311+
6'3"	200-239	240-318	319+
6'4"	205-245	246-327	328+
	1 Point	2 Points	3 Points

You weigh less than the 1 Point column (0 points)

Adapted from Bang et al., Ann Intern Med 151:775-783, 2009. Original algorithm was validated without gestational diabetes as part of the model.

## If you scored 5 or higher

You are at increased risk for having prediabetes and are at high risk for type 2 diabetes. However, only your doctor can tell for sure if you have type 2 diabetes or prediabetes, a condition in which blood sugar levels are higher than normal but not high enough yet to be diagnosed as type 2 diabetes. **Talk to your doctor to see if additional testing is needed.**

[figure not shown]
If you are African American, Hispanic/Latino American, American Indian/Alaska Native, Asian American, or Pacific Islander, you are at higher risk for prediabetes and type 2 diabetes. Also, if you are Asian American, you are at increased risk for type 2 diabetes at a lower weight (about 15 pounds lower than weights in the 1 Point column). Talk to your doctor to see if you should have your blood sugar tested.

[figure not shown]
## You can reduce your risk for type 2 diabetes

Find out how you can reverse prediabetes and prevent or delay type 2 diabetes through a **CDC-recognized lifestyle change program** at <https://www.cdc.gov/diabetes/prevention/lifestyle-program>.

Risk Test provided by the American Diabetes Association and the Centers for Disease Control and Prevention.

[figure not shown]
**11.17 HEMOGLOBIN A1C SCREENING PROTOCOL**

## 11.18 HOME STUDY VISIT APPROPRIATENESS SCREENING PROTOCOL (A1CNow+ SCREENING)

For home study visits, the portable A1CNow+ test kit will be used for measuring A1C. This device is susceptible to interference/inaccuracy from certain underlying conditions. Therefore, the following screening algorithm will be followed to determine whether the participant is appropriate for a home study visit. If not, the participant will be offered the option of a study visit at the clinical research unit.

### Home Study Visit Appropriateness Screening Protocol (A1CNow+ Screening)

**11.19 INCIDENT DIABETES LETTER**

Date

Dear [Name of Clinician],

Your patient [Participant's Name/ DOB] has been a participant in our clinical trial entitled "Effectiveness and Cost-Effectiveness of Fully-Automated Digital vs. Human Coach-Based Diabetes Prevention Programs" since [date of enrollment]. Our trial is comparing two different methods of diabetes prevention (a digital approach vs. standard of care human coach-based DPPs) in overweight adults with prediabetes. This trial lasts 12 months for each participant.

During this study, your patient....

(choose one)

Option #1:

was found to have a point-of-care hemoglobin A1C measurement of \_\_\_\_\_ [list result] on \_\_\_\_\_ [date]. This result was obtained using an over-the-counter test kit (A1CNow+, PTS Diagnostics). We advised your patient to follow-up with you to determine whether additional testing is needed to confirm the diagnosis of diabetes mellitus. Since our study was using an over-the-counter test, we would suggest repeating the A1C test using a serum A1C sample together with a fasting glucose sample for further diagnostic evaluation. However, we would defer to your clinical judgment in determining the need for additional testing.

Option#2: informed our study team that they have been diagnosed with diabetes mellitus.

Please note that your patient will remain eligible to participate in this study even if confirmed to have diabetes or started on any antihyperglycemic medications.

Please feel free to contact our team at [phone] or email the PI, [name], at [[contact]](mailto:[contact]) if you have any additional questions or concerns.

Sincerely,

[name] MHS

Principal Investigator

Associate Professor of Medicine

Division of Endocrinology, Diabetes & Metabolism

Johns Hopkins University School of Medicine

[contact]

[contact]

Email: [[contact]](mailto:[contact])

## 11.20 COVID-19 SAFETY PLAN

### 11.20.1 PRIOR TO STUDY VISIT

- All participants will be asked about COVID-19 symptoms and potential exposures to COVID-19 via phone call by the study coordinator one day before each study visit.
- All participants will be advised to put on a face covering, regardless of symptoms, during the in-person visit.
- Participants will be instructed to notify the study coordinator prior to the visit if they have fever ( $T > 100.4^{\circ}\text{F}$ ) or symptoms of COVID-19. If they have symptoms, we will cancel the visit and participants will be advised to contact their healthcare provider. The study visit will be postponed until they are symptom-free for 14 days.
- All study personnel who will have direct contact with study participants are required to take a daily health screening survey before reporting to work. This is mandatory to protect our research personnel and participants. Any study personnel with symptoms should not report to work.
- We will clean and disinfect all study devices and equipment before use.
- We will follow Johns Hopkins Medicine general guidance and policies related to COVID-19.

### 11.20.2 DURING STUDY VISIT

- Research staff and participants must wear a face covering or mask over the nose and mouth. If the study participant is not already wearing a cloth face covering, we will provide a face mask.
- All study participants will be screened on arrival. They will be asked whether they have a fever ( $T > 100.4^{\circ}\text{F}$ ) or symptoms of COVID-19, including cough or shortness of breath, sore throat, fever, muscle aches, headache, the new loss of taste or smell, repeated or shaking chills. If they have symptoms, we will cancel the visit and participants will be advised to contact their a healthcare provider. The study visit will be postponed until they are symptom-free for 14 days.
- We will maintain social distancing (staying 6 feet or more away from others) between staff and participants whenever possible.
- All study team members will be advised to wash and sanitize hands often.
- We will clean and disinfect all study devices and equipment before use.
- We will follow Johns Hopkins Medicine general guidance and policies related to COVID-19.

## 11.21 ADVERSE EVENT EVALUATION

Have you had any new medical problems since the last visit?	 Yes. Please describe the new medical problem(s).  No
Do you think the medical problem(s) was related to your [use of the Sweetch digital diabetes prevention program/ participation in the DPP]	 Yes. If Yes, Why do you believe the medical problem(s) was related to the [Sweetch DPP/ DPP]?  No

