## 8.3 SAFETY AND OTHER ASSESSMENTS

Since this study is focused on lifestyle modification (physical activity, healthy nutrition, and weight management) for diabetes prevention, it is considered to be a low-risk study with no obvious safety concerns. Participants will be informed of their laboratory results, height, and weight measurements at the study visit.

Participants' individual electronic medical records will be reviewed during screening and assessment of adverse events. Health Insurance Portability and Accountability Act (HIPAA) rules, other relevant federal or state laws, and local institutional requirements should be followed, as applicable.

A brief AE evaluation will be conducted (Section 11.20) at the 6 month and 12 month study visits.

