#### 8.4.4 TIME PERIOD AND FREQUENCY FOR EVENT ASSESSMENT AND FOLLOW-UP

The occurrence of an AE or SAE may come to the attention of study personnel during study visits and interviews of a study subject presenting for medical care, or upon review by a study monitor. All AEs including local and systemic reactions not meeting the criteria for SAEs will be captured on the appropriate CRF. Information to be collected includes event description, time of onset, clinician’s assessment of severity, relationship to study intervention (assessed by clinician), and time of resolution/stabilization of the event. All AEs occurring while on study must be documented appropriately regardless of relationship. All AEs will be followed to adequate resolution.

Any medical condition that is present at the time the subject is screened will be considered as baseline and not reported as an AE. However, if the study subject’s condition deteriorates at any time during the study, it will be recorded as an AE. UPs will be recorded in the data collection system throughout the study.

Changes in the severity of an AE will be documented to allow an assessment of the duration of the event at each level of severity to be performed. AEs characterized as intermittent require documentation of onset and duration of each episode.

The PI will record all reportable events with start dates occurring at any time after informed consent is obtained until 7 (for non-serious AEs) or 30 days (for SAEs) after the last day of study participation. At each study visit, the RC will inquire about the occurrence of AEs/SAEs since the last visit. Events will be followed for outcome information until resolution or stabilization.

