#### 8.4.5 ADVERSE EVENT REPORTING

AEs will likely be reported first to research coordinators during scheduled study visits or during follow-up communications and will be documented in the participant’s electronic case report form.

Research Coordinators are expected to enter adverse event information immediately into REDCap. The Research Coordinator will report the date of onset and resolution of the AE, description of the problem, adverse event preferred term using the MedDRA medical terminology, and the perceived grade of the AE. The Research Coordinator will contact the PI and Project Manager immediately by phone or text message for any perceived Grade 4 or higher AE (life-threatening consequences; urgent intervention indicated, or death related to adverse event). For all AEs entered into REDCap, the PI and project manager will immediately receive an email notification indicating that an adverse event has been reported, prompting further AE assessment. The PI will review the event and determine the grade, relatedness, and adverse event preferred term using the MedDRA medical terminology. If the lead PI ([name]) is not available, the research coordinator will contact the co-investigator ([name]) who will serve as a back-up.

The PI will record all reportable events with start dates occurring at any time after informed consent is obtained until 7 days (Grades 1-2) or 30 days (Grades 3-5) after the last day of study participation. At each study visit, the research coordinator will inquire about the occurrence of AEs since the last visit. Events will be followed for outcome information until resolution or stabilization.

The PI will inform the IRB, DSMB, and NIH program officer immediately when five grade 3 AEs are determined to be “probably related” to the study intervention. The DSMB will convene an ad hoc meeting by teleconference or in writing as soon as possible.

The DSMB will provide recommendations to the study team and sponsor (NIH). If the NIH determines that an unanticipated intervention effect presents an unreasonable risk to subjects, investigations, or parts of investigations presenting that risk will be terminated as soon as possible.

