##### **Costs**

Costs will be estimated using a health system perspective and consist of formal healthcare costs and informal healthcare costs in accordance with best practices. Healthcare costs will be estimated using healthcare resources utilized multiplied by prices for resources. We anticipate that healthcare utilization costs during the trial will be similar between arms. Future healthcare utilization costs will be projected based on previously published literature in relation to our metabolic endpoints. We will use patient reported medical history and medication (Section 11.4) and healthcare utilization (Section 11.14) collected baseline, 6 months, and 12 months during the study to quantify healthcare resources utilized. Unit prices will be derived from public database and Medicare fee schedules. We will use published data to supplement cost data including cost estimates for each health state in the Markov model. Intervention costs will be estimated from data provided to us by the company developing the app, Sweetch Health, Ltd. Costs for the human coach intervention in the hDPP arm will be estimated using the Medicare Diabetes Prevention Program (MDPP) billing and fee schedule.

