## 11.4 MEDICAL HISTORY AND MEDICATIONS

	Past Medical History (resolved)	Active diagnosis or problem
Hypertension (high blood pressure)		
Hypertriglyceridemia (high triglycerides)		
Hyperlipidemia (high cholesterol)		
Coronary artery disease (heart disease)		
Polycystic Ovarian Syndrome (PCOS)		
Smoking		
Depression		
Anxiety		
Bipolar disorder		
Stroke		
Transient ischemic attack (TIA or mini stroke)		
Peripheral vascular disease		
Back pain		
Osteoarthritis		
Hypothyroidism		
Asthma		
Chronic Obstructive Pulmonary Disease (COPD)		
Hepatitis B		
Hepatitis C		
Malignancy		
Insomnia or sleep disorder		
List any other past medical history of active diagnosis/problem not listed above.		

List the generic names of each medication you are currently taking.	
---	--

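### The adverse-event form asks only about new medical problems, although the protocol also counts worsening of an existing condition as an AE

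*Combined protocol and SAP*

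**What the plan says.** Section 8.4.1 defines an AE broadly, as any untoward medical occurrence. Section 8.4.4 then deals with conditions already present at screening. They count as baseline and are not AEs in themselves, but if the participant's "condition deteriorates at any time during the study, it will be recorded as an AE".

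Section 8.3 provides for a brief AE evaluation at the 6- and 12-month visits. The form is in Section 11.21 (Section 8.3 points to 11.20 and the Schedule of Activities to 11.19). It has two items. The first asks "Have you had any new medical problems since the last visit", and a yes leads to a description field ("Please describe the new medical problem(s"). The second asks whether the reported problem was related to the program.

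Four other sources of AE information are described:

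- Section 8.4.5: "At each study visit, the research coordinator will inquire about the occurrence of AEs since the last visit". Section 8.4.4 says much the same.
- Section 8.3: participants' "individual electronic medical records will be reviewed during screening and assessment of adverse events".
- Section 11.4: a history checklist with resolved and active boxes, a free-text line and the item "List the generic names of each medication you are currently taking". Section 9.4.9 (Costs) says these data and the utilization data are "collected baseline, 6 months, and 12 months during the study".
- Section 11.14: counts of visits and admissions, with reasons for some of them, for example "Why did you see a non-primary care specialist".

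Section 9.4.10 reports safety as frequency tables in the ITT population.

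**The concern.** The form is narrower than the rule it serves. Section 8.4.4 makes deterioration of a baseline condition an AE, yet the only scripted AE question in the protocol does not ask about it. Someone with long-standing knee osteoarthritis that flared after more walking has an AE by the protocol's definition but no new medical problem. They could answer no in good faith. The relatedness item would then not apply, so the form would also hold no view on whether the program contributed.

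This class of event is relevant here. Both programs promote physical activity, and Section 8.4.3.3 names muscle soreness, fatigue and musculoskeletal injury as the anticipated AEs. Section 11.4 lists back pain, osteoarthritis, asthma, COPD and coronary disease among the conditions participants may bring to the study. What is at stake is whether the safety tables count such events.

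**Working it through.** The point turns on wording, so the check sets the rule beside each route by which a worsened baseline condition could reach the AE record.

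| Route | Does it ask about worsening? |
|---|---|
| 11.21, item 1 and description field | No. Both are limited to new problems. |
| 11.21, item 2 | No. It asks only about the relatedness of problems already reported. |
| Coordinator inquiry (8.4.4, 8.4.5) | Possibly. No wording is given, and the protocol does not say whether the inquiry is separate from 11.21. |
| Record review (8.3) | Only if the worsening reached a chart the team can see. Recruitment also runs through mailings, radio, social media and community events, and 11.3 takes a record number only for patients in the health system. |
| History and medications (11.4) | Indirectly. A condition active at baseline and active but worse at month 12 is ticked the same way. A new drug would show. A dose increase would not, because only generic names are listed. |
| Utilization (11.14) | Partly. Reasons are asked for specialist, ED and hospital care, but for primary care only the number of visits. |

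What remains is mainly worsening that led to no new drug, no specialist, ED or hospital care and no visible chart entry, and that the coordinator's inquiry does not draw out. Dose increases, and primary care outside the two health systems, can fall into the same gap.

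The number of forms involved follows from Section 9.2 and the Schedule of Activities:

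- Scheduled: 2 × 368 = 736.
- Retained at month 12 under the planned 25% attrition: 0.75 × 368 = 276.
- Completed if nobody leaves before month 6: 368 + 276 = 644.
- Completed if all attrition falls before month 6: 2 × 276 = 552.
- Recall period: about 180 days to the first follow-up visit, then 365 − 180 = 185 days to the second. The ±14-day windows allow 185 − 28 = 157 to 185 + 28 = 213 days for the second period.

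The completed-form figures assume that everyone still in the study attends each visit, so 552 is not a strict minimum. They show how often the question is put, not how many events are lost. The documents give no rate at which baseline conditions worsen, so the loss cannot be computed.

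**The case against.** The best defence is that 11.21 is only a brief evaluation and nothing makes it the sole source of AEs. Section 8.4.4 governs and already obliges staff to record deterioration. Beyond the routes tabulated above:

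- AEs may surface in follow-up communications (8.4.5), and staff contact participants around each roughly monthly ActiGraph period.
- A study monitor's review can bring events to light (8.4.4).
- Chest pain or shortness of breath during activity requires further medical clearance (2.3.3, 8.4.3.3), which covers the deterioration of most concern in an activity trial.
- The Manual of Procedures named in 10.1.12 may contain fuller wording for the inquiry.

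Safety output is descriptive, and the protocol regards the study as low risk.

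Much of this stands as a limit on the size of the problem. Serious worsening, or worsening that leads to care, has several chances of being found. It does not remove the mismatch. The monthly contacts are not scripted for AEs, and the clearance rule concerns two symptoms only. An obligation to record deterioration helps only if staff hear of it. The Manual was not available for this review, so suitable wording there cannot be excluded.

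**Conclusion.** The concern holds, as a minor point. As written, the form leaves out a class of events that the protocol itself defines as AEs. That much is certain from the text. How many events would be lost is unknown, and depends on how the coordinator's inquiry is worded in practice and on what the Manual of Procedures says.

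The consequence is possible under-counting in the safety tables of Section 9.4.10. Because both arms receive the same question, there is no clear reason to expect a bias between them. No hypothesis test, sample-size figure or efficacy result depends on this.

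**What to change.** In Section 11.21, insert *or worsened* after *new* in the opening question and again in the description field. The relatedness item refers to the problem without the word *new* and can stay as it is. No extra item, contact or visit is needed. The cross-references to this form in Section 8.3 and the Schedule of Activities could be corrected to 11.21 at the same time.

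The cost is two words in two places, plus the routine consequences. More AEs will be recorded, in a number that cannot be predicted. Each is entered in REDCap, triggers a notice to the PI and project manager, and is coded, graded, assessed for relatedness and followed to resolution (8.4.4, 8.4.5). If the change is made as a protocol amendment, it needs IRB approval first (10.1.2). If some follow-up forms have already been completed, the date of the change should be recorded so that AE counts before and after it can be read correctly.
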